5.4. Analysis sets

Analysis sets and its definitions are described in this section. The analysis set will be identified and included as a subtitle of each TLF.

The following treatment groups will be used for analysis: CT-P59 20 mg/kg, CT-P59 40 mg/kg, CT-P59 80 mg/kg and placebo. For placebo group, pooling of patients assigned to placebo treatment within each cohort is considered for analysis.

For Intent-to-treat (ITT) set, patients will be assigned to either “CT-P59 20 mg/kg”, “CT-P59 40 mg/kg”, “CT-P59 80 mg/kg” or placebo treatment group according to the treatment they were randomized to. The PK and Safety sets will be analyzed according to actual treatment group. Patients receiving at least one kit of CT-P59 will be assigned to the actual treatment group of CT-P59 of corresponding cohort, even if the patient is randomized to placebo group.

The number and percentage of patients in all sets will be tabulated by the treatment group on ITT set. A listing will also be produced displaying data on ITT set.

5.4.1. Intent-to-Treat Set

The ITT set is defined as all patients enrolled and randomly assigned to receive a dose of either of the study drugs, regardless of whether or not any study drug dosing was completed.

5.4.2. Safety Set

The safety set will consist of all patients who receive a full or partial dose of the study drugs.

5.4.3. Pharmacokinetic Set

The PK set will consist of all patients who receive a full dose of CT-P59 and have at least 1 evaluable post-treatment PK concentration result.

5.5. Definition of Baseline

The baseline value will be considered to be the last non-missing value before the study drug administration. Post-baseline values will be considered to be all measurements collected after the study drug administration.

5.6. Protocol Deviations

Protocol deviation will be categorized as “major” or “minor”. A major protocol deviation is one that may affect the interpretation of study results or the patient’s rights, safety or welfare, and will be identified prior to study unblinding. Major protocol deviations include, but are not limited to, the following:

- Mis-randomization (defined as patients who received treatment other than randomly assigned treatment)
- Non-adherence to Inclusion or Exclusion criteria (to be identified through review of data)
- Significant Good Clinical Practice (GCP) non-compliance

A listing of major protocol deviations for each patient will be provided by treatment group for the ITT set.

5.7. Outliers

Any outliers that are detected during the review of the data will be investigated and discussed during the DRM. In general, outliers will not be excluded.

6. PATIENT DISPOSITION

The number of patients who were screened will be displayed. The number of patients who failed at screening will be also displayed along with the primary reason for screening failure based on the ‘Eligibility Criteria’ page of eCRF.

The number and percentage of patients who were randomized, initiated study treatment, completed the period including EOT, discontinued the period including EOT will be displayed for the ITT set with percentage by treatment group.

Patient disposition will be defined as follows:

- A patient will be considered to have failed the Screening if the screening failure date is recorded on the ‘Eligibility Criteria’ page of eCRF.
- A patient will be considered to be randomized if a randomization ID was allocated to the patient based on the ‘Randomization’ page of eCRF.
- A patient will be considered to be initiated study treatment if it is recorded as ‘Yes’ to study drug administration on the ‘Study Drug Administration’ page of eCRF.
- A patient will be considered to have completed the treatment period including EOT if it is recorded that the patient was completed from the study (‘Yes’ box checked) on the ‘End of Treatment Period’ page of eCRF.
- A patient will be considered to have discontinued the treatment period including EOT if it is recorded that the patient was discontinued from the study (‘No’ box checked) on the ‘End of Treatment Period’ page of eCRF.

The number and percentage of patients who discontinued the treatment period including EOT and ended the study participation including follow-up period will be displayed by primary reason for discontinuation and ending participation based on the ‘End of Treatment Period’ and ‘End of Study Participation’ page of eCRF, and treatment group respectively.

In addition, time on study prior to discontinuation will be displayed using descriptive statistics, for those patients who initiate the study treatment and discontinue. Time on study to end of study participation will be displayed using descriptive statistics, for those patients who initiate the study treatment and end.

The study duration in days will be calculated as (study discontinuation date [for end of study participation, end of study participation date] – study drug administration date + 1). The study discontinuation date, end of study participation date and study drug administration date will be taken as the date on the ‘End of Treatment Period’ page, ‘End of Study Participation’ page and on the ‘Study Drug Administration’ page of eCRF respectively.

Patient disposition data will be listed for the ITT set by treatment group. A listing will also be provided to display data from ‘Eligibility Criteria’ page of eCRF.

7. DEMOGRAPHICS, BASELINE, AND BACKGROUND CHARACTERISTICS

7.1. Demographics and Stratification Details

The following demographic measures and stratification details will be summarized for the ITT set: Age (years); Sex (Male, Female); Fertility Status (Pre-Menarche, Surgically Sterilized, Post-Menopausal, and Potentially Able to Bear Children. For female patient only); Race (White, Black or African American, American Indian or Alaska Native, Asian, Native Hawaiian or

Other Pacific Islander, Not Allowed by Investigator Country Regulations, Other); Ethnicity (Hispanic or Latino, Non-Hispanic or Non-Latino, Unknown); Height (cm), Weight (kg) and Body Mass Index (BMI) (kg/m^2) as recorded at Screening.

Age will be automatically calculated in eCRF system based on the date of the informed consent day and the year of birth considering whether birth date has passed the informed consent date or not.

Demographics will be listed for the ITT set by treatment group.

7.2. Viral Serology Test

At Screening, the following assessments for serologic markers will be performed:

- Hepatitis B Surface Antigen (HBsAg)
- Hepatitis B Core Antibody (HBcAb)
- Hepatitis C Antibody
- Human Immunodeficiency Virus (HIV) -1 and -2

All viral serology test result will be listed for ITT set by treatment group.

7.3. Urine Drug Test

A urine drug test will be performed at Screening. The screen for drug abuse includes methamphetamine, barbiturates, benzodiazepines, cocaine, tetrahydrocannabinol, and opiates. The urine test can be repeated once at the discretion of the Investigator. All urine drug test result will be listed for the ITT set by treatment group.

7.4. Medical History

Medical history is captured at Screening and will be coded using Medical Dictionary for Regulatory Activities (MedDRA Version 23.0 or the later version). Medical history will be summarized by treatment group, system organ class (SOC) and preferred term (PT) for the ITT set. Medical history will be listed for the ITT set by treatment group.

7.5. Disease Characteristic

Disease characteristic is captured at Screening visit. The number and percentage of patients with symptoms will be summarized by treatment group for the ITT set. Time (days) since the earliest symptom start will be calculated as (date of study drug administration – date of earliest symptom start). Time (days) since the earliest symptom start will be summarized by treatment group using descriptive statistics. All disease characteristic will be listed for the ITT set by treatment group.

8. TREATMENTS AND MEDICATIONS

8.1. Prior and Concomitant Medications

All medications used during the study, taken within 30 days before the patient signs the ICF until the EOT visit will be collected on the eCRF. All medications will be coded according to the World Health Organization drug dictionary (WHO Drug Dictionary March 2020 or the later version). Medications will be classified as either prior or concomitant.

A prior medication is defined as following, and all other medications will be defined as concomitant medication.

- A medication checked as “Yes” to “If stop date is unknown, was this drug stopped before the study drug administration (Day 1)?” on eCRF or
- A medication having stop date of medication before the date of study drug administration.

The prior medications will be summarized by treatment group, drug class (using Anatomical Therapeutic Chemical [ATC] level 2), and PT along with the total number of prior medications and the number and percentage of patients with at least one prior medication for the Safety set. The separate tables will be also generated for the concomitant medications by treatment group, drug class (using ATC level 2), and PT along with the total number of concomitant medications and the number and percentage of patients with at least one concomitant medication for the Safety set. At each level of summarization, a patient is counted only once if the patient reported one or more medications at that level. When ATC Level 2 for drug class is not available, Level 1 will be used instead.

All prior and concomitant medications will be listed separately by treatment group for the Safety set.

8.2. Exposure to Study Drug

The number and percentage of patients who received the study drugs will be summarized by treatment group for the Safety set. The prescribed and actual administered dose (mg) of study drug will also be summarized using descriptive statistics.

A listing will be provided by treatment group for the ITT set showing the details collected on the “Study Drug Administration” page of eCRF.

8.3. Study Restriction Assessment

Patients who follow or not any of the study restriction will be listed for the Safety set by

treatment group, visit and category.

9. VIROLOGY ANALYSIS

Virology analysis will be conducted on the ITT set unless otherwise stated.

Virology analysis consists of viral efficacy (viral shedding based on qPCR), characterization of SARS-CoV-2 viral isolate (genotyping) and RT-PCR. Viral shedding (qPCR) and genotype samples will be analyzed at the central laboratory and RT-PCR sample will be analyzed at the local laboratory.

If the patient had RT-PCR result confirming SARS-CoV-2 infection prior to obtaining written informed consent (but no more than 7 days from the onset of symptoms), the result can be allowed. During the Screening Period, only one retest for RT-PCR will be allowed, if study drug can be administered no more than 7 days from onset of symptom based on retest results.

Nasopharyngeal swab samples for virology analysis will be collected and corresponding virology analysis will be performed at the time point specified in [Appendix 1](#) and [Appendix 2](#).

Viral titers will be assessed in log₁₀cp/mL for qPCR. The following [Table 2](#) presents how viral titers will be treated in descriptive summary and AUC calculation, and categorized to Positive or Negative.

Table 2 Handling of Viral Titers (qPCR)

	Treated as	Classified as
Quantitative value	Reported value	Positive
BLQ	LLoQ	Positive
Negative	0	Negative

Abbreviations: qPCR= quantitative polymerase chain reaction; BLQ=below the low limit of quantification; LLoQ=lower limit of quantification. NA= Not Applicable.

Actual results and change from baseline for viral shedding in nasopharyngeal swab specimens (titers) for qPCR will be summarized by treatment groups at each scheduled time point. The number and percentage of patients with positive / negative for qPCR will also be summarized by treatment group and scheduled time point.

Duration (days) of viral shedding in nasopharyngeal swab specimens for qPCR will be calculated as (date/time of post-baseline last positive sample - date/time of study drug administration). Patients with at least one positive sample after baseline will be included in the summary. Duration of viral shedding for qPCR will be summarized by treatment groups using descriptive statistics.

AUC of viral titers for qPCR is calculated from date/time of study drug administration to date/time of last measurable value of patients who have at least one post-baseline result

(including BLQ and negative values) using linear trapezoidal rule. Viral titer at baseline will be considered as result at study drug administration. AUC of viral titers for qPCR will be summarized by treatment groups using descriptive statistics.

Mean (\pm SD) viral titer of qPCR for each scheduled time point will be plotted by treatment group.

All virology results including qPCR and RT-PCR will be listed for each patient by treatment group and time point respectively.

Genotype results will be listed by treatment group in patients with predose sample with $> 3 \log_{10}$ cp/mL in ITT set. Day 1 (SARS-CoV-2 positive sample) and the last SARS-CoV-2 positive sample in time with $> 3 \log_{10}$ cp/mL will be analyzed. Additional samples were analyzed if SARS-CoV-2 infection symptoms were deteriorated or viral titers were not noticeably reduced.

The first CSR will present viral shedding in nasopharyngeal swab specimens based on qPCR up to Day 7 of each patient displaying descriptive statistics for actual results and change from baseline, and frequency table for categorized results and figure for mean (\pm SD) of viral titer. All virology analysis will be presented in the Final CSR.

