### **3.4.3 End-of-Treatment Visit (Day 90)**

End-of-treatment (EOT) visit assessments will be performed on Day 90. Patients will undergo the assessments specified in [Table 11-1](#) and [Table 11-2](#).

If a patient early terminated from the study, the patient will be asked to return to the study center for the safety assessments predefined on an EOT visit.

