**Table 6-2 Nasopharyngeal Swap Sampling Time Points for Virology Assessment**

Day	Time point	Window
Screening*	Anytime	Day -7 to Day 1
Day 1*	Predose	Predose within the day
Day 2	24 hours after start of infusion	
Day 3	48 hours after start of infusion	
Day 4	72 hours after start of infusion	
Day 5	96 hours after start of infusion	± 4 hours
Day 6	120 hours after start of infusion	
Day 7	144 hours after start of infusion	
Day 10	216 hours after start of infusion	
Day 14	312 hours after start of infusion	± 1 day
Day 21	480 hours after start of infusion	
Day 28	648 hours after start of infusion	± 3 days

\* If Screening and administration of study drug are occurred on the same day, sampling of nasopharyngeal swab will be performed twice both for RT-PCR (local) of Screening and viral shedding and genotype (central) of Day 1, respectively.

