Clinical recovery is defined by all symptoms on the SARS-CoV-2 infection symptom Checklist are recorded as ‘absent’ or ‘mild’ in intensity for at least 24 hours. To satisfy the clinical recovery, symptoms of the moderate or severe in intensity at baseline should be scored as mild or absent, or symptoms of the mild or absent in intensity at baseline should be scored as absent, after study treatment. Patients who meet the clinical recovery criteria for at least three consecutive time points will be considered as satisfying condition of 24 hours, and achieving clinical recovery at the first time point. The three consecutive time points for each symptom can be different because the three consecutive time points will be determined excluding missing data if the results of some symptoms are missing on the SARS-CoV-2 infection symptom Checklist. However, results of all 7 symptoms have to be recorded at the first time point achieving clinical recovery. The example of a patients achieving clinical recovery on Day 14 Morning is presented the following [Table 3](#).

Table 3 Example of a Patients Achieving Clinical Recovery

	Day 14 Morning	Day 14 Evening	Day 15 Morning	Day 15 Evening
Feeling feverish	0	0	Missing	0
Cough	0	Missing	0	0
Shortness of breath or difficulty breathing	0	0	0	0
Sore throat	0	0	0	0
Body pain or muscle pain	0	0	0	0
Fatigue	0	0	0	0
Headache	0	0	0	0

The time to clinical recovery (days) will be calculated as [date/time achieving clinical recovery (or censoring) – date/time of study drug administration]. Patients who are ongoing in the study without event, with death or early withdrawal for any reason will be considered as censored at the day of their scheduled visit of interest (Day 28). Missing time of completion of diary will be assumed to be 10:00 AM and 10:00 PM for calculation of time to recovery.

The number and percentage of patients with clinical recovery up to Day 7, Day 14, and Day 28 and Censored up to Day 28 along with censoring reason will be displayed by treatment group. The 25th percentile, 50th percentile (median) and 75th percentile will be estimated from Kaplan-Meier curve for the time to clinical recovery up to Day 28 and displayed by treatment group. Kaplan-Meier plots for each treatment group will be presented.

This listing will include all data collected on the “SARS-CoV-2 Infection Symptom Checklist” page of eCRF.

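### SAP 9 enters a still-positive last swab as a completed shedding duration and leaves out the fastest clearers; viral AUC lacks an end rule for early leavers

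*SAP*

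**What the plan says.** SAP section 9 defines duration of shedding as "date/time of post-baseline last positive sample - date/time of study drug administration". On who counts, it says "Patients with at least one positive sample after baseline will be included in the summary". On method, it says "Duration of viral shedding for qPCR will be summarized by treatment groups using descriptive statistics". No later negative swab is required, and no rule covers a patient whose last swab is positive.

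Viral AUC runs from dosing "to date/time of last measurable value of patients who have at least one post-baseline result" ("including BLQ and negative values) using linear trapezoidal rule"). SAP Table 2 sets a negative result to 0 and a result below quantification to the LLoQ.

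The last listed swab in Protocol Table 6-2 is Day 28, "648 hours after start of infusion". For a patient who stops early, Protocol 3.4.3 says "the patient will be asked to return to the study center for the safety assessments predefined on an EOT visit"; the SAP schedule lists no swab at that visit.

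Protocol 7.4.4 names duration and AUC among the virology summaries but gives no formula. SAP 13.1 does not mention them. For time to clinical recovery, SAP 10.1 does handle incomplete follow-up: "Patients who are ongoing in the study without event, with death or early withdrawal for any reason will be considered as censored", with Kaplan-Meier quartiles and plots.

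**The concern.** Two features of the duration rule act in opposite directions on its level.

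- **Down.** If the last swab is positive, the end of shedding is unknown. The recorded number is only a lower limit, yet it enters the mean and median as if complete.
- **Up.** A patient positive at baseline and negative at every later swab has one of the shortest durations, and is dropped although the stated set is ITT.

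For AUC, a still-positive patient who leaves early accumulates less area than the same patient followed to Day 28, so leaving early looks like a lower viral burden.

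Viral efficacy is the first secondary objective, and groups are 5, 5, 5 and 3 (pooled placebo), so one patient is 20% to 33% of a group. Groups that differ in withdrawal or in very early clearance may not be comparable on these two summaries.

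**Working it through.** The plan states no expected duration, AUC or dropout rate, so there is no figure to reproduce. Shedding times and dropout below are assumptions.

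**Inputs from the documents.** Post-dose swabs at 24, 48, 72, 96, 120, 144, 216, 312, 480 and 648 hours, i.e. 1, 2, 3, 4, 5, 6, 9, 13, 20 and 27 days after infusion. Gaps after Day 7 are 3, 4, 7 and 7 days. Five active patients per cohort; 3 × 1 = 3 placebo.

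**1. Constructed group of five, all positive at baseline.** A is negative at every later swab. B is last positive at 6 days and negative at 9. C is last positive at 13 and negative at 20. D is positive at 27. E withdraws after a positive swab at 6.

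- SAP rule: A is dropped. Mean (6 + 13 + 27 + 6)/4 = 13.0; median (6 + 13)/2 = 9.5.
- Kaplan-Meier, clearance at the midpoint between swabs: events at 0.5 (A), 7.5 (B) and 16.5 (C); E censored at 6, D at 27. Survival is 4/5 = 0.80, then 0.80 × 2/3 = 0.533, then 0.533 × 1/2 = 0.267. The median is 16.5. The mean restricted to 27 days is 0.5 + 7 × 0.80 + 9 × 0.533 + 10.5 × 0.267 = 13.7.
- Kaplan-Meier, clearance at the first negative swab: median 20.

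Here the two errors nearly cancel in the mean but not in the median, and the clearance convention matters.

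**2. Average size.** Assumed: Weibull times (shape 1.5), planned swabs, dropouts leaving uniformly 1 to 27 days after dosing; 400,000 simulated patients per row. All values are days except the last column.

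| True median | True mean, restricted to Day 28 swab | Planned mean, 0% / 20% dropout | SD of 5-patient mean | At least 1 of 5 positive at last swab, 0% / 20% |
|---|---|---|---|---|
| 1 | 1.15 | 1.34 / 1.34 | – | – |
| 2 | 2.31 | 2.30 / 2.28 | – | – |
| 3 | 3.46 | 3.27 / 3.22 | – | – |
| 7 | 8.1 | 7.0 / 6.7 | 2.1 | 3% / 31% |
| 10 | 11.3 | 9.8 / 9.2 | 2.9 | 21% / 51% |
| 14 | 14.8 | 13.1 / 12.2 | 3.6 | 57% / 76% |
| 20 | 18.4 | 16.9 / 15.4 | 3.9 | 87% / 93% |

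The last column is 1 − (1 − c)^5, with c the share still positive; at median 20 with no dropout, 1 − (1 − 0.337)^5 = 87%.

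The net bias is upward at a median of 1 day, about zero at 2 and downward from 3. Without dropout, the shortfall comes from counting only to the last positive swab, which groups with equal clearance share. Dropout of 20% takes off a further 0.3, 0.5, 1.0 and 1.5 days at medians 7, 10, 14 and 20. If departures occur only after the Day 7 swab, that becomes about 0.1, 0.4, 0.7 and 1.2.

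This yardstick stops at Day 28. Against the unrestricted mean the shortfall is larger when shedding is long: at a median of 21 days, under exponential or lognormal times, a true mean of 26.8 to 30.4 becomes 17.3 to 17.8. Swabs ending at Day 28 cannot recover that without a model for the tail.

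**3. The exclusion alone.** Patients with no post-baseline positive are 50%, 22%, 3.7% and 0.8% at medians 1, 2, 7 and 20. Dropping them rather than counting 0 raises the mean by 0.67, 0.50, 0.26 and 0.13 days.

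**4. AUC.** Assume 6 log10 falling 0.3 per day, linear trapezoid, floor 0. To the Day 7 swab: 6 × (6 + 4.2)/2 = 30.6. To Day 28: 20 × 6/2 = 60.0. One such leaver changes a 5-patient mean to (4 × 60.0 + 30.6)/5 = 54.1 (−10%) and a 3-patient mean to (2 × 60.0 + 30.6)/3 = 50.2 (−16%). For declines of 0.6 to 0.2 per day the ranges are 4–13% and 6–21%. With patient variation (baseline SD 1, slope SD 0.1), 20% dropout lowers the mean from 67.9 to 63.2 (−7%), against an SD of 13.6 for a 5-patient mean.

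**5. Does censoring repair it?** The midpoint Kaplan-Meier restricted mean, at 0% / 20% dropout, is 1.17 / 1.17 (true 1.15), 11.4 / 11.4 (11.3), 14.9 / 14.9 (14.8) and 18.4 / 18.4 (18.4) at medians 1, 10, 14 and 20. This holds when withdrawal is unrelated to shedding, as simulated.

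**The case against.** The strongest case for the plan is that it is open about what it measures and that little is hidden.

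- **Visibility.** A reader might infer that the omitted and still-positive patients cannot be seen in the report. The documents do not support that. SAP 5 requires n with every continuous summary; SAP 9 tabulates positives and negatives by visit and lists each patient's qPCR results; SAP 6 reports discontinuations. The number omitted follows from n. What remains is that the duration summary itself treats lower limits as complete.
- **Who is omitted.** A reader might infer that everyone left out cleared fast. Undosed patients, patients with no post-baseline swab and patients negative on central qPCR at baseline are also left out, and they have no defined duration. Some restriction is therefore needed. The upward bias comes only from patients positive at baseline and never afterwards.
- **Protocol wording.** Protocol 7.4.4 asks for descriptive statistics or frequency tables, and duration is not a named endpoint as time to recovery is. That is true, but it does not turn a lower limit into a completed duration.
- **Dropout.** The 20% is assumed (3.6 of 18 patients). Patients are confined for at least 72 hours, Day 7 is recommended, and replacement is allowed for non-safety reasons. This stands, and shrinks the withdrawal part as shown.
- **AUC.** A reader might infer that no two patients share an AUC end. If a negative counts as measurable, completers share a nominal Day 28 end and zeros after clearance add nothing. Only early leavers, missed late swabs and the meaning of measurable are at issue.

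**Conclusion.** The point holds and is minor. SAP 9 states a rule under which lower limits are averaged as completed durations and the fastest clearers are dropped, while the same SAP censors clinical recovery in the same small groups.

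Net direction and size depend on shedding and dropout rates that the documents do not give. Under the Weibull assumptions the gap from the Day 28-restricted mean is 1.1 to 3.0 days at medians 7 to 20 (8.1 − 7.0 without dropout; 18.4 − 15.4 with 20%), below the SD of a 5-patient mean in each row. Chance variation is larger still in 3 placebo patients.

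A reader might infer that the rule favours or penalises CT-P59. If the drug shortens shedding, both errors would act toward no difference, but that is conditional on facts the documents do not contain.

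No hypothesis test or sample size depends on these outputs. The by-visit summaries and the first CSR, which shows qPCR to Day 7 without duration or AUC, are unaffected.

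**What to change.** In SAP 9, with the change recorded in SAP 13.1:

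1. **Duration.** Analyse shedding through Day 28 as time to event in dosed patients with a positive central qPCR at baseline or later and at least one post-baseline swab. Right-censor at the last swab if it is positive (at that swab, not at Day 28 as SAP 10.1 does for recovery). Count patients positive at baseline and never afterwards as cleared by their first negative swab. Report Kaplan-Meier quartiles where reached, or the mean restricted to Day 28. State where clearance is placed between swabs: the midpoint is reasonable, whereas the first negative swab shifts times upward (20.1 for a true restricted mean of 18.4).
2. **Counts.** Beside the summary, give the number still positive at the last swab and the number with no post-baseline positive, by reason. If nothing else changes, add this and flag both in the listing.
3. **AUC.** State that negatives count as measurable. Use fixed windows, dosing to Day 7 and dosing to Day 28, with the number contributing. A patient whose last swab is negative takes 0 to the window end; early leavers whose last swab is positive are shown separately. Do not divide by observed time: on the trajectory above that gives 30.6/6 = 5.1 for a Day 7 leaver and 60.0/27 = 2.2 for a completer.

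The cost is SAP wording and reprogramming of two derived variables, with no new data. The drawbacks are real: quantiles may not be reached, estimates are coarse with 5 or 3 patients, the midpoint is a convention across gaps of up to 7 days, censoring assumes withdrawal is unrelated to shedding, and setting still-positive leavers apart from the Day 28 AUC is itself a selection.
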